# Appendix III – Response Evaluation Criteria in Solid Tumors (RECIST) Quick Reference (CTEP)

## **Eligibility**

 Only patients with measurable disease at baseline should be included in protocols where objective tumor response is the primary endpoint.

**Measurable disease** - the presence of at least one measurable lesion. If the measurable disease is restricted to a solitary lesion, its neoplastic nature should be confirmed by cytology/histology.

**Measurable lesions** - lesions that can be accurately measured in at least one dimension with longest diameter ≥20 mm using conventional techniques or ≥10 mm with spiral CT scan.

**Non-measurable lesions** - all other lesions, including small lesions (longest diameter <20 mm with conventional techniques or <10 mm with spiral CT scan), i.e., bone lesions, leptomeningeal disease, ascites, pleural/pericardial effusion, inflammatory breast disease, lymphangitis cutis/pulmonis, cystic lesions, and also abdominal masses that are not confirmed and followed by imaging techniques; and.

- All measurements should be taken and recorded in metric notation, using a ruler or calipers. All baseline
  evaluations should be performed as closely as possible to the beginning of treatment and never more than 4
  weeks before the beginning of the treatment.
- The same method of assessment and the same technique should be used to characterize each identified and reported lesion at baseline and during follow-up.
- Clinical lesions will only be considered measurable when they are superficial (e.g., skin nodules and palpable lymph nodes). For the case of skin lesions, documentation by color photography, including a ruler to estimate the size of the lesion, is recommended.

#### Methods of Measurement -

- CT and MRI are the best currently available and reproducible methods to measure target lesions selected for
  response assessment. Conventional CT and MRI should be performed with cuts of 10 mm or less in slice
  thickness contiguously. Spiral CT should be performed using a 5 mm contiguous reconstruction algorithm. This
  applies to tumors of the chest, abdomen and pelvis. Head and neck tumors and those of extremities usually
  require specific protocols.
- Lesions on chest X-ray are acceptable as measurable lesions when they are clearly defined and surrounded by aerated lung. However, CT is preferable.
- When the primary endpoint of the study is objective response evaluation, ultrasound (US) should not be used to measure tumor lesions. It is, however, a possible alternative to clinical measurements of superficial palpable lymph nodes, subcutaneous lesions and thyroid nodules. US might also be useful to confirm the complete disappearance of superficial lesions usually assessed by clinical examination.
- The utilization of endoscopy and laparoscopy for objective tumor evaluation has not yet been fully and widely
  validated. Their uses in this specific context require sophisticated equipment and a high level of expertise that
  may only be available in some centers. Therefore, the utilization of such techniques for objective tumor response
  should be restricted to validation purposes in specialized centers. However, such techniques can be useful in
  confirming complete pathological response when biopsies are obtained.
- Tumor markers alone cannot be used to assess response. If markers are initially above the upper normal limit, they must normalize for a patient to be considered in complete clinical response when all lesions have disappeared.
- Cytology and histology can be used to differentiate between PR and CR in rare cases (e.g., after treatment to
  differentiate between residual benign lesions and residual malignant lesions in tumor types such as germ cell
  tumors).

#### Baseline documentation of "Target" and "Non-Target" lesions

- All measurable lesions up to a maximum of five lesions per organ and 10 lesions in total, representative of all involved organs should be identified as *target lesions* and recorded and measured at baseline.
- Target lesions should be selected on the basis of their size (lesions with the longest diameter) and their suitability for accurate repeated measurements (either by imaging techniques or clinically).
- A sum of the longest diameter (LD) for *all target lesions* will be calculated and reported as the baseline sum LD. The baseline sum LD will be used as reference by which to characterize the objective tumor.
- All other lesions (or sites of disease) should be identified as non-target lesions and should also be recorded at
  baseline. Measurements of these lesions are not required, but the presence or absence of each should be noted
  throughout follow-up.

#### **Response Criteria**

#### **Evaluation of target lesions**

* Complete Response (CR):	Disappearance of all target lesions
* Partial Response (PR):	At least a 30% decrease in the sum of the LD of target lesions, taking as reference the baseline sum LD
* Progressive Disease (PD):	At least a 20% increase in the sum of the LD of target lesions, taking as reference the smallest sum LD recorded since the treatment started or the appearance of one or more new lesions
* Stable Disease (SD):	Neither sufficient shrinkage to qualify for PR nor sufficient increase to qualify for PD, taking as reference the smallest sum LD since the treatment started

#### **Evaluation of non-target lesions**

* Complete Response (CR):	Disappearance of all non-target lesions and normalization of tumor marker level
* Incomplete Response/ Stable Disease (SD):	Persistence of one or more non-target lesion(s) or/and maintenance of tumor marker level above the normal limits
* Progressive Disease (PD):	Appearance of one or more new lesions and/or unequivocal progression of existing non-target lesions (1)

(1) Although a clear progression of "non-target" lesions only is exceptional, in such circumstances, the opinion of the treating physician should prevail and the progression status should be confirmed later on by the review panel (or study chair).

#### **Evaluation of best overall response**

The best overall response is the best response recorded from the start of the treatment until disease progression/recurrence (taking as reference for PD the smallest measurements recorded since the treatment started). In general, the patient's best response assignment will depend on the achievement of both measurement and confirmation criteria

Target lesions	Non-Target lesions	New Lesions	Overall response
CR	CR	No	CR
CR	Incomplete response/SD	No	PR
PR	Non-PD	No	PR
SD	Non-PD	No	SD
PD	Any	Yes or No	PD
Any	PD	Yes or No	PD
Any	Any	Yes	PD

- Patients with a global deterioration of health status requiring discontinuation of treatment without objective
  evidence of disease progression at that time should be classified as having "symptomatic deterioration". Every
  effort should be made to document the objective progression even after discontinuation of treatment.
- In some circumstances it may be difficult to distinguish residual disease from normal tissue. When the evaluation of complete response depends on this determination, it is recommended that the residual lesion be investigated (fine needle aspirate/biopsy) to confirm the complete response status.

#### Confirmation

- The main goal of confirmation of objective response is to avoid overestimating the response rate observed. In cases where confirmation of response is not feasible, it should be made clear when reporting the outcome of such studies that the responses are not confirmed.
- To be assigned a status of PR or CR, changes in tumor measurements must be confirmed by repeat
  assessments that should be performed no less than 4 weeks after the criteria for response are first met. Longer
  intervals as determined by the study protocol may also be appropriate.
- In the case of SD, follow-up measurements must have met the SD criteria at least once after study entry at a minimum interval (in general, not less than 6-8 weeks) that is defined in the study protocol

#### **Duration of overall response**

The duration of overall response is measured from the time measurement criteria are met for CR or PR
(whichever status is recorded first) until the first date that recurrence or PD is objectively documented, taking as
reference for PD the smallest measurements recorded since the treatment started.

#### **Duration of stable disease**

- SD is measured from the start of the treatment until the criteria for disease progression are met, taking as reference the smallest measurements recorded since the treatment started.
- The clinical relevance of the duration of SD varies for different tumor types and grades. Therefore, it is highly
  recommended that the protocol specify the minimal time interval required between two measurements for
  determination of SD. This time interval should take into account the expected clinical benefit that such a status
  may bring to the population under study.

#### Response review

• For trials where the response rate is the primary endpoint it is strongly recommended that all responses be reviewed by an expert(s) independent of the study at the study's completion. Simultaneous review of the patients' files and radiological images is the best approach.

### Reporting of results

- All patients included in the study must be assessed for response to treatment, even if there are major protocol treatment deviations or if they are ineligible. Each patient will be assigned one of the following categories: 1) complete response, 2) partial response, 3) stable disease, 4) progressive disease, 5) early death from malignant disease, 6) early death from toxicity, 7) early death because of other cause, or 9) unknown (not assessable, insufficient data).
- All of the patients who met the eligibility criteria should be included in the main analysis of the response rate.
   Patients in response categories 4-9 should be considered as failing to respond to treatment (disease progression). Thus, an incorrect treatment schedule or drug administration does not result in exclusion from the analysis of the response rate. Precise definitions for categories 4-9 will be protocol specific.
- All conclusions should be based on all eligible patients.
- Sub-analyses may then be performed on the basis of a subset of patients, excluding those for whom major
  protocol deviations have been identified (e.g., early death due to other reasons, early discontinuation of treatment,
  major protocol violations, etc.). However, these sub-analyses may not serve as the basis for drawing conclusions
  concerning treatment efficacy, and the reasons for excluding patients from the analysis should be clearly
  reported.
- The 95% confidence intervals should be provided.

# **Appendix IV – Targeted Toxicity Worksheet**

See	Section	10.2	for	time	points

based on CTCAE v5

Patient Initials o	r ID:	Date of Assessment: Assessment Time Point:				
ADL = activities o	f daily livir	ng				
Toxicity	Grade 0	Grade 1	Grade 2	Grade 3	Grade 4	
Injection site reaction	None	Tenderness with or without associated symptoms (e.g., warmth, erythema, itching)	Pain; lipodystrophy; edema; phlebitis	Ulceration or necrosis; severe tissue damage; operative intervention indicated	Life-threatening consequences; urgent intervention indicated	
Flu-like symptoms*	None	Mild flu-like symptoms present	Moderate symptoms; limiting instrumental ADL	Severe symptoms; limiting instrumental ADL		
*includes fever, chills,	body aches,	malaise, loss of appetite and	dry cough			
Fatigue	None	Fatigue relieved by rest	Fatigue not relieved by rest; limiting instrumental ADL	Fatigue not relieved by rest, limiting self care ADL		
Fever	None	38.0 - 39.0° C (100.4 - 102.2° F)	> 39.0 - 40.0°C (102.3 - 104.0°F)	> 40.0 ∘ C (>104.0∘ F) for ≤ 24 hrs	> 40.0 ° C (>104.0° F) for > 24 hrs	
Headache	None	Mild pain	Moderate pain; limiting instrumental ADL	Severe pain; limiting self care ADL		
Palpitations	None	Mild symptoms; intervention not indicated	Intervention indicated			
Nausea	None	Loss of appetite without alteration in eating habits	Oral intake decreased without significant weight loss, dehydration or malnutrition	Inadequate oral caloric or fluid intake; tube feeding, TPN, or hospitalization indicated		
Vomiting	None	Intervention not indicated	Outpatient IV hydration; medical intervention indicated	Tube feeding, TPN, or hospitalization indicated	Life-threatening consequences; urgent intervention indicated	
Diarrhea	None	Increase of <4 stools per day over baseline; mild increase in ostomy output compared to baseline	Increase of 4 - 6 stools per day over baseline; moderate increase in ostomy output compared to baseline; limiting instrumental ADL	Increase of >=7 stools per day over baseline; hospitalization indicated; severe increase in ostomy output compared to baseline; limiting self care ADL	Life-threatening consequences; urgent intervention indicated	
Constipation	None	Occasional or intermittent symptoms; occasional use of stool softeners, laxatives, dietary modification, or enema	Persistent symptoms with regular use of laxatives or enemas; limiting instrumental ADL	Obstipation with manual evacuation indicated; limiting self care ADL	Life-threatening consequences; urgent intervention indicated	
Other Skin/ Subcutaneous – Specify	None	Per CTCAE v5 criteria	Per CTCAE v5 criteria	Per CTCAE v5 criteria	Per CTCAE v5 criteria	
		eting This Form:				

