# **Study Schema**

1 cycle = 3 weeks (21 days) with a 2-cycle minimum unless medically contraindicated.

**HCW9218** at assigned dose by subcutaneous (SC) injection once every 3 weeks until disease progression, unacceptable toxicity, patient refusal, or felt to be no longer of benefit

Assess for Dose Limiting Toxicity (DLT) at Cycle 2 Day 1 (defined below and in Section 6.3)

tumor biopsy (baseline and prior to Cycle 3) – optional, in participants with accessible tumor who have signed the separate biopsy consent (Tumor used for biopsy should not be a RECIST target lesions unless there are no other lesions suitable for biopsy.)

Disease reassessment per disease specific standard of care (i.e. every 8-12 weeks)

Phase I HCW9218 Dose Levels			
Dose Level (DL)	HCW9218 dose		
-1*	0.1 mg/kg		
1 (start)	0.25 mg/kg		
2	0.5 mg/kg		
3	0.8 mg/kg		
4	1.2 mg/kg		

\* use only if excessive toxicity encountered at DL1

**Dose limiting toxicity (DLT)** is defined as any of the following **treatment emergent events** based on CTCAE v5 within 21 days after the 1st dose of HCW9218 as assessed on Day 22 (Cycle 2 Day 1) per Section 6.3.

DLT event	Exceptions:			
Any Grade 4 hematologic event	
 
Grade 4 lymphopenia that resolves to Grade 1 or lower (or to Baseline or lower, if pre-existing Grade 2 or higher) within 7 days
 
Grade 4 leukopenia that resolves to Grade 1 or lower (or to Baseline or lower, if pre-existing Grade 2 or higher) within 7 days
 
			
Any Grade 3 or Grade 4 febrile neutropenia				
Any Grade 3 thrombocytopenia with bleeding				
Any Grade 3 or higher non-hematologic adverse event	
 
Grade 3 nausea, vomiting and/or diarrhea that last < 72 hours
 
Grade 3 or higher electrolyte abnormality that lasts < 72 hours, is not clinically complicated, and resolves spontaneously or responds to conventional medical interventions
 
Isolated Grade 3 elevation of ALT and/or AST that resolves to Grade 1 or lower (or to Baseline or lower, if pre-existing Grade 2 or higher) within 7 days
 
Grade 3 amylase or lipase that is not associated with symptoms or clinical manifestations of pancreatitis
 
Grade 3 fatigue, not due to disease progression, that lasts < 1 week
 
			

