# 6.2.1 STAGE 1 STEP 1 - Fast-track design (1 patient per dose level)

Start at DL1, enroll 1 patient per DL separated by a minimum of 21 days (DLT period) until the:

- 1st pre-defined adverse event Any of the following treatment emergent Grade 2 events lasting >72 hours within 5 days of 1st dose of HCW9218: fatigue, flu-like symptoms or injection site reaction.
- And the patient completes the 21 day DLT period with no DLT- Activate
   Stage 1 Step 2 in Section 6.2.2.

OR

1st DLT event within 21 days after the 1st dose of HCW9218 - Activate
 Stage 2 in Section 6.2.3 - Stage 1 Step 2 is not used.

OR

• 9 patients are treated at the DL4 - This completes enrollment - Stage 1 Step 2 and Stage 2 are not used.

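### The Targeted Toxicity Worksheet sets the same functional limit for flu-like symptoms at Grade 2 and Grade 3, a boundary that can decide between a DLT and no DLT, and nothing says which grading source prevails

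*Combined protocol and SAP*

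**What the plan says.** Appendix IV is headed as based on CTCAE v5. Under Section 10.2.2 it is completed on Cycle 1 Day 1 (before the injection and at 3 and 6 hours), Day 2, Day 3 and Day 5. It records the highest grade since the last assessment, which for outpatients may be reported by the patient. Its flu-like row covers fever, chills, body aches, malaise, loss of appetite and dry cough. Grade 2 is "Moderate symptoms; limiting instrumental ADL"; Grade 3 is "Severe symptoms; limiting instrumental ADL".

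Two rules use these grades:

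- **Step 2 trigger (Section 6.2.1).** The pre-defined events are "Grade 2 events lasting >72 hours within 5 days of 1st dose of HCW9218: fatigue, flu-like symptoms or injection site reaction". If the patient also completes the 21-day period without a DLT, the trial moves to Stage 1 Step 2.
- **DLT (Study Schema and Section 6.3).** The definition includes "Any Grade 3 or higher non-hematologic adverse event" within 21 days of the first dose. The listed exceptions cover nausea, vomiting, diarrhea, electrolytes, ALT/AST, amylase or lipase, and fatigue. Flu-like symptoms are not among them.

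Section 6.3 grades toxicity by CTCAE v5, except where Section 10 notes otherwise. Section 10 also names CTCAE v5, and Section 10.2.2 says the worksheet is done in addition to AE documentation.

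**The concern.** A patient whose flu-like symptoms limit instrumental ADL but not self care fits the functional wording of both cells. The grader has only the adjective to go on. In most grading tables a soft boundary between adjacent grades matters little, but here it is a decision threshold. One score leaves the DLT count unchanged. The other adds a DLT, ends Stage 1 and starts the CRM. The primary endpoint is the MTD, which is determined from DLTs, so a false one would enter the primary result.

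The form also gives staff little reason to look elsewhere, because it presents itself as CTCAE v5 grading.

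**Working it through.** No sample size, power or event count is involved, so the check is a comparison of text. The plan gives no figure on this point to reproduce.

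**Step 1: compare the worksheet rows that use ADL at both grades (Appendix IV).**

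| Row | Grade 2 limit | Grade 3 limit | Grade 3 wording |
|---|---|---|---|
| Fatigue | instrumental ADL | self care ADL | "Fatigue not relieved by rest, limiting self care ADL" |
| Headache | instrumental ADL | self care ADL | "Severe pain; limiting self care ADL" |
| Diarrhea | instrumental ADL | self care ADL | stool count, hospitalization and ostomy criteria, plus self care ADL |
| Constipation | instrumental ADL | self care ADL | "Obstipation with manual evacuation indicated; limiting self care ADL" |
| Flu-like symptoms | instrumental ADL | instrumental ADL | "Severe symptoms; limiting instrumental ADL" |

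Four of the five rows move to self care ADL. The flu-like row alone does not.

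**Step 2: follow one patient through the rules.** Take flu-like symptoms that limit instrumental ADL only, starting soon after the first dose, with no other event.

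| Situation | Scored Grade 2 | Scored Grade 3 |
|---|---|---|
| Step 1, more than 72 hours within 5 days | Step 2 activated, 0 DLTs | 1 DLT, Stage 2 activated, Step 2 not used |
| Step 1, 72 hours or less | nothing triggered, 0 DLTs | 1 DLT, Stage 2 activated |
| Step 2, any duration | nothing triggered, 0 DLTs | 1 DLT, Stage 2 activated |
| Stage 2, any duration | 0 DLTs in the CRM update | 1 DLT in the CRM update |

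The choice between Step 2 trigger and DLT therefore arises only in the first situation. In the other three the choice is between no consequence and a DLT.

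**Step 3: see whether another rule settles the grade.**

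- Section 6.3 and the opening of Section 10 name CTCAE v5, which points to formal AE grading as decisive.
- Section 6.3 leaves room for whatever Section 10 notes differently, and the worksheet is set out in Section 10.2.2.
- The table in Section 10.2 lists DLTs, AEs of Grade 2 or higher, and the worksheet as separate rows, without ranking them.
- Section 11.4 requires each patient's DLT status to be documented after the first 21 days, but does not say which grading source that review uses.

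The overall direction is clear, but no sentence states the order of precedence.

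**Step 4: see whether the size can be estimated.** It cannot. The documents give no rate of misgrading between Grades 2 and 3. Section 13.3 says the complete skeleton estimates are not determined until Stage 2, so a misgraded event cannot be carried through to Table 2.

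**The case against.** The strongest reply is that the worksheet does not define a DLT. CTCAE v5 does, the sheet is supplementary, and the team reviews every patient with the investigator and statistician expected to attend. The two cells are also not identical, since moderate and severe still differ. All of this stands, and it makes an uncorrected error less likely. It does not supply a precedence rule or repair the row.

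The record to date also supports the reply. The revision entry of March 29 2023 states that no DLTs had been observed from dose level 1 to dose level 4. A Grade 3 flu-like event accepted in the window would have been one. The exposure is therefore for later patients at dose level 4 and for any CRM stage.

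A reader might infer three stronger things that the documents do not support:

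- **That the MTD is biased downward.** A false DLT could act that way, but the CRM continues to assign cohorts against the 25% target, and its response to one extra DLT cannot be computed without the skeleton.
- **That this row will be used often.** Section 7.2 lists flu-like symptoms as common, but without regard to grade and for similar drugs. Section 7.1 reports that subcutaneous delivery of a related IL-15 agent produced no acute constitutional symptoms, and HCW9218 is given subcutaneously.
- **That the effect can be sized by assuming a misgrading rate and comparing the trial-level result with a DLT rate in Table 2.** Any such rate would be unsourced, and Table 2's rates are per patient. Taken at trial level with its own Expected patient numbers (1, 1, 1 and 9) and independent patients, Table 2 already implies 1 − 0.9925 × 0.985 × 0.97 × 0.93^9 = 1 − 0.494, about 51%, for at least one DLT.

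**Conclusion.** The inconsistency is plain on the page and falls on a decision threshold, so it should be corrected. It makes it possible for an event limiting only instrumental ADL to be recorded as Grade 3 and counted as a DLT; one such event in Stage 1 would be enough to activate Stage 2. The probability of this, and its effect on the selected MTD, cannot be estimated from the documents. No DLT had been recorded by the March 2023 revision.

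The conclusion rests on two readings. First, flu-like symptoms fall under the general Grade 3 non-hematologic rule because no exception names them. Second, the worksheet grade can inform DLT documentation, which the documents neither require nor rule out. That self care ADL was the intended Grade 3 limit is inferred from the sheet's own parallel rows; the CTCAE v5 text is not reproduced in the documents.

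**What to change.** 1. Reconcile the Grade 3 flu-like cell in Appendix IV with CTCAE v5, which the sheet says it follows, and with the pattern of its other ADL rows. Take the wording from the CTCAE v5 source itself.
2. Add one sentence to Section 10.2.2: if the worksheet and CTCAE v5 grading differ, CTCAE v5 grading decides both the Step 2 trigger and DLT status.
3. Check any Grade 3 flu-like worksheet entry against CTCAE v5 before it counts as a DLT, and record the outcome in the DLT review under Section 11.4.

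The cost is one worksheet cell, one sentence, and a check of any such entries. No dose, schedule, sample size or analysis changes.
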